## Appendix 6 Medical Events Commonly Associated with Peritoneal Dialysis

The following are medical events that have been commonly reported as possibly related to PD therapy in general:

Abdominal pain:	A generic term for focal or general discomfort localized to the abdominal region.
Back pain:	Pain felt in or along the spine or musculature of the posterior thorax.
Bleeding:	The escape of blood from an injured vessel.
Chest pain:	A general term for any dull, aching pain in the thorax, usually referring to that of acute onset, which is often regarded as being myocardial in origin unless proven otherwise.
Drain pain (outflow pain):	A sense of abdominal discomfort; pain or crampy discomfort arising during the drain phase of a peritoneal dialysis exchange that may occur during a manual or automated peritoneal dialysis exchanges.
Edema (Peripheral and/or facial; Scrotal):	An abnormal accumulation of fluid in intercellular spaces of the body.
Fever:	A fever is any body temperature elevation over 100 °F (37.8 °C).
Headache:	Pain in the head which can arise from many disorders or may be a disorder in and of itself.
Hematuria:	Presence of blood or red blood cells in the urine.
Hernia:	Protrusion of a part or structure through the tissues normally containing it.
Hydrothorax:	Accumulation of serous fluid in one or both pleural cavities.
Hypertension:	Persistently high arterial blood pressure.
Hypoglycemia:	An abnormally low level of glucose in the blood.
Hypotension:	Persistently low arterial blood pressure.
Itching:	An uncomfortable sensation of irritation of the skin or mucous membranes that causes scratching or rubbing of the affected parts.
Chills:	A sensation of cold, with convulsive shaking of the body.
Muscle cramps:	A sudden and involuntary contraction of one or more muscles
Nausea:	An unpleasant sensation vaguely referred to the epigastrium and abdomen, with a tendency to vomit.
PD catheter leak:	An appearance of any moisture around the PD catheter identified as dialysate.
Vomiting:	The ejection of matter from the stomach in retrograde fashion through the esophagus and mouth.

---

This list does not include medical events that are part of the exclusion criteria and/or should always be considered an AE regardless of medical history, severity or frequency.

---

---

## Appendix 7 New York Heart Association Functional Classification

NYHA Functional Classification	
NYHA Class	Patients with Cardiac Disease (Description of HF Related Symptoms)
Class I (Mild)	Patients with cardiac disease but without resulting in limitation of physical activity. Ordinary physical activity does not cause undue fatigue, palpitation (rapid or pounding heart beat), dyspnea (shortness of breath), or anginal pain (chest pain).
Class II (Mild)	Patients with cardiac disease resulting in slight limitation of physical activity. They are comfortable at rest. Ordinary physical activity results in fatigue, palpitation, dyspnea, or anginal pain
Class III (Moderate)	Patients with cardiac disease resulting in marked limitation of physical activity. They are comfortable at rest. Less than ordinary activity causes fatigue, palpitation, dyspnea, or anginal pain.
Class IV (Severe)	Patients with cardiac disease resulting in the inability to carry on any physical activity without discomfort. Symptoms of heart failure or the anginal syndrome may be present even at rest. If any physical activity is undertaken, discomfort is increased.

---

2. LIST OF ABBREVIATIONS AND DEFINITIONS OF TERMS

ADE	Adverse Device Effect
AE	Adverse Event
AESI	Adverse Event of Special Interest
APD	Automated Peritoneal Dialysis
BMI	Body Mass Index
BP	Blood Pressure
CFU	Colony Forming Units
DD	Device Deficiency
eCRF	Electronic Case Report Form
ESRD	End Stage Renal Disease
EU	Endotoxin Units
ICF	Informed Consent Form
MedDRA	Medical Dictionary for Regulatory Activities
PC	Product Complaint
PD	Peritoneal Dialysis
PI	Principal Investigator
PT	Preferred Term
RO	Reverse Osmosis
SADE	Serious Adverse Device Effect
SAE	Serious Adverse Event
SAP	Statistical Analysis Plan
SGS	Solution Generation System
SOC	System Organ Class
TAMC	Total Aerobic Microbial Count
TEAE	Treatment-Emergent Adverse Event
TYMC	Total Combined Yeast and Mold Count
WD	Water Device

3. INTRODUCTION

This statistical analysis plan (SAP) is provided to describe the framework for the reporting, summarization, and statistical analysis methodology of the safety and efficacy parameters measured throughout the study. It is based on clinical trial protocol BXU011787 Amendment 6, dated 01NOV2019.

Peritoneal dialysis (PD) is a well-established treatment for renal failure including long-term management of end stage renal disease (ESRD) by continuous ambulatory peritoneal dialysis or automated peritoneal dialysis (APD). It is a procedure for removal of uremic toxins which are normally excreted by the kidneys, and for aiding the regulation of fluid and serum electrolytes as well as acid-base balance. In patients with renal failure, during PD, uremic toxins, present in high concentrations in the blood, cross the peritoneal membrane into the dialyzing fluid, according to the principles of osmosis and diffusion. Peritoneal dialysis solutions contain variable amounts of glucose, all of them being hyperosmolar to the plasma, creating an osmotic gradient which facilitates fluid removal from the plasma to the solution.

The AMIA APD Solution Generation System consists of the AMIA APD Cycler, Sharesource Platform, AMIA APD Concentrates (a Dextrose Concentrate and an Electrolyte Concentrate), a disposable set (containing a cassette, a water line with holding bag and two sterilizing grade filters, a heater bag, a patient line, a dextrose concentrate line, a last fill solution line, an electrolyte concentrate line, and a drain line), a bag tray, a Water Softener (also referred to as the Ion Exchanger), and a Water Device (WD). The WD consists of a pre-treatment filter pack, reverse osmosis (RO) membrane, heater, conductivity and temperature sensors, and ports for a patient connection. The Water Softener is an accessory to the WD.

The AMIA APD Solution Generation System combines an updated AMIA APD Cycler with Sharesource Platform (previously cleared under K151525) with an in-home water system technology and leverages newly developed AMIA APD Concentrates.

The AMIA APD Solution Generation System is intended for automatic control of dialysis solution exchanges in the treatment of adult renal failure patients undergoing PD in home or clinic environments.

The AMIA APD Solution Generation System is a drug-device combination product. All therapies using the AMIA APD Solutions Generation System must be prescribed and performed under the responsibility of a physician who is well informed about PD and the study system.

The system is designed to produce dialysis solution as prescribed by the clinician. The resulting AMIA APD Generated Solution will be mixed from the sterile AMIA APD Concentrates (a Dextrose Concentrate and an Electrolyte Concentrate) and sterile, non-pyrogenic water (post-sterilizing filters). AMIA APD Generated Solution is formulated to have a nominal solution chemistry that is equivalent to the labeled composition of Dianeal Low Calcium (2.5 mEq/L), in three standard dextrose strengths (1.5%, 2.5% and 4.25%).

The AMIA APD Concentrates, after dilution by the AMIA APD Solution Generation System, are indicated for adult patients in acute or chronic renal failure when non-dialytic medical therapy is judged to be inadequate.

- The AMIA APD Concentrates are only intended to be used together, and only as a part of the AMIA APD Solution Generation System.
- The Dextrose Concentrate is a sterile, non-pyrogenic product used in the preparation of the AMIA APD Generated Solution when using the AMIA APD Solution Generation System.
- The Electrolyte Concentrate is a sterile, non-pyrogenic product containing the electrolytes and buffer used in the preparation of the AMIA APD Generated Solution when using the AMIA APD Solution Generation System.

4. TRIAL OBJECTIVES

4.1 Primary Objectives

Efficacy

To evaluate the chemical composition of the final dialysis solution produced by patients using the AMIA APD Solution Generation System during simulated treatment, compared to the specifications of Baxter's approved Dianeal Low Calcium (2.5 mEq/L) PD Solution.

Safety

To evaluate the product water from the WD (pre-sterilizing filters) as meeting ISO standard 13959¹ for microbiological (including endotoxin) and chemical contamination, and water in the holding bag (post-sterilizing filters) as meeting system microbiological requirements, when produced in patients' homes using the AMIA APD Solution Generation System, during a simulated treatment.

4.2 Secondary Objectives

- To evaluate the safety of the AMIA APD Solution Generation System, used to treat patients with ESRD, by collecting adverse events (AEs), serious adverse events (SAEs), adverse device effects (ADEs), serious adverse device effects (SADEs), incidence of device alarms and vital signs.
- To assess PD adequacy by calculation of total Kt/V_{urea} .

5. STUDY DESIGN

5.1 Study Design

This is an open-label, single arm, prospective, descriptive study. Up to 50 PD patients, who are stable on in-home APD using the AMIA APD Cyclor or HomeChoice APD Cyclor, will be enrolled in this study such that a total target of 30 evaluable patients complete the 12-week Study Treatment Period and the Follow-up Period.

The group of patients who withdrew prior to the completion of the treatment period and corresponding follow-up visits will be considered as *early terminated*, and the corresponding reason for termination will be recorded. The complimentary group of patients who complete the full study period (treatment + follow-up) will be considered as *completed*.

5.2 Sample Size

A formal sample size calculation was not performed. Up to 50 patients will be enrolled such that a total target of 30 evaluable patients complete the 12-week Study Treatment Period and the Follow-up Period.

5.3 Randomization Procedure

Not applicable, as this is a single arm study.

5.4 Schedule of Visits and Procedures

During the Screening Period, all consenting patients will have a home assessment, including feed (tap) water analysis, to confirm their home environment is suitable for this study. Eligible patients will be followed for data collection regarding dialysate solution composition and safety while using the AMIA APD Solution Generation System.

Data will be collected throughout the duration of the study (approximately 18 weeks), including the Screening Period, Baseline Period (In-center Training Period), Study Treatment Period, Follow-up Period and the End-of-Study Visit/ Early Termination Visit.

[figure not shown]

All AEs (not reported as medical history), product complaints (PCs) and device deficiencies (DDs) observed by the study personnel or reported by the patient during the course of the study will be documented from the time of signing the informed consent form (ICF) through the End-of-Study/ Early Termination Visit. The Principal Investigator (PI) or designee (e.g., sub-investigator) will assess each patient at the Screening Visit and on a weekly basis, according to standard of care. At a minimum, this assessment will include evaluation of blood pressure (BP), pulse rate, weight, fluid status and dialysis prescription.

Laboratory data will be collected at screening and during the use of the AMIA APD Solution Generation System.

Evaluations will be taken as illustrated in Appendix 1. A trial scheme for the study is shown in Figure 1 below.

Figure 1. Overview of Study Assessments

5.5 Efficacy Measures

5.5.1 Primary Endpoints

Primary efficacy endpoint is:

- Testing of the chemical composition of the final dialysis solution produced by patients using the AMIA APD Solution Generation System, during simulated treatment, compared to the specifications of Baxter’s approved Dianeal Low Calcium (2.5 mEq/L) PD Solution.

Primary safety endpoints are:

- Microbiological (including endotoxin) and chemical testing of product water from the WD (pre-sterilizing filters) per ISO Standard 13959.¹
- Microbiological testing of water in the holding bag (post-sterilizing filters) to confirm that the water does not exceed 0 colony forming units (CFU) /mL for bacteria (no growth) and is <0.03 endotoxin units (EU)/ mL for endotoxins, consistent with Dianeal specifications for sterility.

5.5.2 Secondary Endpoint(s)

- Safety profile of the AMIA APD Solution Generation System used to treat patients with PD by collecting AEs, SAEs, adverse device effects (ADEs), SADEs, incidence of device alarms and vital signs.
- Peritoneal dialysis adequacy will be measured by sample collection and calculation of total Kt/V_{urea} , occurring once at any time during weeks 5, 6, 7 or 8 of the Study Treatment Period.

6. GENERAL STATISTICAL CONSIDERATIONS

Unless otherwise specified, summary statistics (n, arithmetic mean, standard deviation [SD], median, minimum, and maximum values) will be presented for continuous variables. Counts and, if relevant, percentages will be presented for categorical variables.

Unless otherwise specified, all data tables, listings, and figures will be on all patients in the Safety Set (as defined in [section 7.2](#))

Unless otherwise specified, data listings will include site ID, patient ID, sex, age at screening (rounded down to the nearest whole number), race, and baseline weight.

Unless otherwise specified, the estimated mean and median for a set of values will be displayed to 1 more significant digit than the original values, standard deviations will be displayed to 2 more significant digits, and minimum and maximum values will be displayed with the same number of significant digits as the original values. All percentages will be displayed out to 1 decimal places.

Unless otherwise noted, all analyses will be performed using SAS/Graph® 9.4 software, SAS/STAT® 15.1 software, and BaseSAS® 9.4. Copyright © 2016, SAS Institute Inc. SAS and all other SAS Institute Inc. product or service names are registered trademarks or trademarks of SAS Institute Inc., Cary, NC, USA. All Rights Reserved

7. DISPOSITION

7.1 Patient Disposition

Patient disposition will be summarized and will include:

- Number of patients who signed informed consent
- Number of patients enrolled (defined as having a home installation and meeting all eligibility criteria)
- Number of patients treated
- Number of patients in the Safety Set
- Number of patients who completed the study
- Number of patients who discontinued (withdrew early) from the study and subsequently re-enrolled. These patients will also be summarized by primary reason for withdrawal from the study. The percentages associated with each reason for early withdrawal will have the total number of patients who withdrew early and re-enrolled as the denominator
- Number of patients who discontinued and did not subsequently re-enroll. The percentage associated with this will be the number of patients who withdrew and did not re-enroll.

Patients who withdrew early from the study will be listed, and the listing will include the number of days that the patient remained in the study, the primary reason from withdrawal, and whether the patient re-enrolled.

All disposition tables and listings will be based on the set of all patients who signed informed consent.

7.2 Analysis Populations

The Safety Set is based on the intent-to-treat principle and will include all patients who have received at least one treatment with the AMIA APD Solution Generation System and who have at least one measurement for the primary endpoint (either primary efficacy or primary safety).

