### **10.3 Analysis Populations**

The Safety Set is based on the intent-to-treat principle and will include all patients who have received at least one treatment with the AMIA APD Solution Generation System and who have at least one measurement for the primary endpoint (either primary efficacy or primary safety).

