### **10.7 Sensitivity Analysis**

A sensitivity analysis of the primary safety endpoint of product water from the water device may be performed using the results of the home installation test in lieu of missing Simulated Treatment Visit 1 data.

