14.2 Adverse Events (AEs)

14.2.1 General

Summaries of AEs will be presented using counts and percentages for the safety set.

Tables by preferred term and tables by system organ class (SOC) and preferred term will be sorted in descending order by the percentage of patients.

For all adverse event analyses, the date of first treatment will refer to the first date the patient ever received treatment with the Point of Care device. If a patient had stopped treatment then re-started, the date that they first started (including prior enrollments) will be used as the date of first treatment.

Unless otherwise specified, the summaries of adverse events will include the total number of patients experiencing the adverse event, the total number of events, and the adverse event rate (number of events per patient year). The total number of patient years will be calculated as follows for all adverse events (including pretreatment AEs):

$$\frac{\sum_{i=1}^n (\text{Date of Study Completion/Withdrawal} - \text{Informed Consent Date}) + 1}{365.25},$$

where n represents all patients in the Safety Set.

The total number of patient years will be calculated as follows for all treatment-emergent adverse events:

$$\frac{\sum_{i=1}^n (\text{Date of Study Completion or Withdrawal} - \text{Date of first treatment}) + 1}{365.25},$$

where n represents all patients in the Safety Set.

The adverse event rate will be calculated as:

$$\frac{\text{Total Number of Events}}{\text{Total patient years}}$$

For summaries of AEs presented by severity, the maximum severity will be presented if patients have multiple AEs within a SOC and preferred term (PT) with varying severity. If the severity of an adverse event is missing, then that adverse event will be classified as *severe*.

For summaries of AEs presented by relationship, the most conservative relationship will be presented if patients have multiple AEs within a SOC and PT with different relationships to either study product or typical PD therapy.

For patients who had re-enrolled, all adverse events will be listed and summarized.

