14.3 Other Safety Data

14.3.1 General

Unless otherwise specified, tables, listings, and figures will be based on the Safety Set.

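### The Safety Set requires a water or solution result as well as treatment, so a treated patient without one would be missing from every adverse-event table: a rare case, and cheap to close

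*SAP*

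**What the plan says.** SAP 7.2 sets two conditions for the Safety Set. The first, based on exposure, takes in "all patients who have received at least one treatment with the AMIA APD Solution Generation System". The second is joined to it and keeps only those "and who have at least one measurement for the primary endpoint (either primary efficacy or primary safety"). Protocol 10.3 and the protocol synopsis carry the same two-part definition: the patient must be treated and must be among those "who have at least one measurement for the primary endpoint (either primary efficacy or primary safety"). No other analysis set is defined.

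This set is assigned to the clinical safety outputs at several levels:

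- SAP 6 makes it the general default: "Unless otherwise specified, all data tables, listings, and figures will be on all patients in the Safety Set". Adverse-event and death listings fall under this default.
- SAP 14.2.1 applies it to adverse events: "Summaries of AEs will be presented using counts and percentages for the safety set". Both patient-year formulas there sum over the same patients: "where n represents all patients in the Safety Set".
- SAP 14.3.1 applies it to the remaining safety data, including vital signs: "Unless otherwise specified, tables, listings, and figures will be based on the Safety Set". SAP 14.3.2 names it again for device deficiencies and uses it for the device-day denominator.
- Protocol 10.6 assigns the adverse-event, alarm and vital-sign summaries to it.

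Two other passages point the other way. Protocol 6.8 says that for patients removed early, whatever data are available go into all analyses. SAP 7.3 says that data gathered before discontinuation are used in the analysis and the study report.

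**The concern.** A safety population should contain everyone exposed. The second condition has no connection with exposure. The primary-endpoint measurements are laboratory results on water and solution from simulated treatments, during which the patient is not connected (protocol 6.5.7). Whether a courier sample reached the laboratory should not decide whether a patient's serious adverse event is tabulated.

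A treated patient outside the set would be missing from the adverse-event tables and listings, the patient-years, the device-deficiency and alarm summaries and the vital signs. Exclusion can fall only on patients who also have no later sample, which in practice means those who leave early. The withdrawal reasons in SAP 7.3 include adverse event, death, inadequate dialysis and water device replacement, so an excluded patient may be one whose events matter.

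**Working it through.** The plan gives no figure to reproduce: there is no formal sample size calculation, and no dropout or missing-sample rate. The check is to trace what exclusion requires and then show the scale under stated assumptions.

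**Step 1: what must happen for a treated patient to be excluded.**

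- Protocol 5.3 places the first simulated treatment before the first home treatment. SAP 16.3 gives a window of up to 7 days before Day 1.
- Visit 1 yields three kinds of sample: heater-bag solution, product water and holding-bag water (protocol 8.6). A result on any one satisfies the definition.
- The next scheduled sampling is in Week 4 (SAP 16.3).

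Exclusion therefore needs both (a) no Visit 1 result of any of the three types and (b) departure before any Week 4 result.

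**Step 2: is that route open?** Yes, narrowly. Home treatment is conditional on the post-installation product-water results (protocol 6.5.8.1 and 6.5.8.2), not on Visit 1 results. Protocol 10.7 foresees an analysis "using the results of the home installation test in lieu of missing Simulated Treatment Visit 1 data", so missing Visit 1 product water is contemplated. Footnote v of the schedule of events keeps Screening tests out of the analysis. The SAP also classes a test as missing if any parameter was not tested (13.2, 14.1.2, 14.1.3), and the product-water panel has 27 parameters. It does not say whether a partly tested sample still counts as a measurement; a strict reading would widen the gap.

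**Step 3: how many patients?** The inputs are assumptions. Let m be the probability of no Visit 1 result of any type, taken as 2% to 10%, and d the probability of leaving before Week 4, taken as 5% to 20%, independent of m. Then q = m × d, the expected number excluded is N × q, and P(at least one) = 1 − (1 − q)^N.

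| N treated | m | d | q | Expected excluded | P(at least one) |
|---|---|---|---|---|---|
| 50 | 2% | 5% | 0.1% | 0.05 | 4.9% |
| 50 | 5% | 10% | 0.5% | 0.25 | 22.2% |
| 50 | 10% | 20% | 2.0% | 1.0 | 63.6% |
| 30 | 2% | 5% | 0.1% | 0.03 | 3.0% |
| 30 | 5% | 10% | 0.5% | 0.15 | 14.0% |
| 30 | 10% | 20% | 2.0% | 0.6 | 45.5% |

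Fifty is the enrolment ceiling and 30 the target for completers. If one problem, such as a faulty device, caused both the missing samples and the departure, independence would fail and q would be larger.

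**Step 4: effect of one excluded patient on a percentage (assumed counts).**

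- Patient with a serious event, the only one in the study: 1/50 = 2.0% becomes 0/49 = 0.0%. With 30 treated, 1/30 = 3.3% becomes 0/29 = 0.0%.
- Patient with a serious event, one of four: 4/50 = 8.0% becomes 3/49 = 6.1%.
- Event-free patient: 4/50 = 8.0% becomes 4/49 = 8.2%.

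**The case against.** The strongest reply is that the schedule largely prevents the problem. A patient who follows it has been sampled three ways before being exposed, so leaving early does not by itself remove anyone. A reader might infer from protocol 10.7 and SAP 14.1.2 that the plan expects patients with no Visit 1 data at all. It does not: both passages concern missing product water only, and such a patient would normally still qualify through the solution or the holding bag. This part of the reply stands, and it is why the problem should be rare.

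It can also be argued that the installation test closes the gap, since every compliant patient has a reviewed product-water result before home treatment. Footnote v excludes tests done in Screening, but installation may also fall in the Baseline Period, and the endpoint text sets no visit for product water. On the other side, the primary safety objective refers to simulated treatment, and the installation result is brought in only for a sensitivity analysis. The point is arguable, and a safety population should not depend on it.

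Third, the gap would be visible. SAP 7.1 bases disposition on all consented patients, counts those treated and those in the Safety Set, and lists each early withdrawal with its reason. That would reveal an omission, but disposition does not present adverse events. The test-result listings for all enrolled patients do not either.

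Finally, protocol 6.8 and SAP 7.3 suggest that the sponsor did not intend to drop anyone. They conflict with the definition without amending it, so the texts still need to be reconciled.

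**Conclusion.** The point holds as a defect in the definition. The only analysis set ties clinical safety reporting to a laboratory sample, and a treated patient with no sample result would appear in no adverse-event, alarm, device-deficiency or vital-sign output.

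Its expected size is small. Under the assumed ranges, between 0.05 and 1.0 of 50 treated patients would be excluded, and it may well be none. Those rates are not in the documents. The consequence for a single patient is not trivial in a study this small, because an only serious event could vanish from the tables.

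Two stronger readings are not supported. A reader might conclude that the definition biases every adverse-event figure towards a safer system. The direction depends on who is omitted: transfer to another center, a boil-water advisory and voluntary withdrawal are also listed reasons, and omitting an event-free patient raises the percentage. A reader might also picture a large distortion, such as 6/50 = 12.0% falling to 4/48 = 8.3%. That needs two patients, each without any Visit 1 result, each gone before a Week 4 result and each with a serious event. On the assumptions above with 50 treated, the chance of even two exclusions is about 0.1% to 26%, before asking that both had such events.

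This is a low-cost correction worth making, not a critical fault in a descriptive study without hypothesis tests.

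**What to change.** Define the Safety Set as all patients treated at least once with the system, and use it for every clinical safety output: adverse events, deaths, patient-years, device deficiencies, alarms, vital signs and laboratory data. Apply the measurement condition only to the primary-endpoint tables, where a result is needed in any case.

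Make the same edit in SAP 7.2, protocol 10.3 and the protocol synopsis. That brings all three into line with protocol 6.8 and SAP 7.3, and the status of partly tested samples and installation results no longer affects who is counted for safety. If the protocol is not amended, record the change in SAP 12, since protocol 10.1 provides for changes of method to be documented in the SAP.

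The cost is one sentence in each of three places. No new data, visits or samples are needed, and if nobody would have been excluded the results do not change.
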